8.3 Sample Size Considerations

The sample size of the trial ensures that sufficient safety and immunogenicity data will be available in a population with co-morbidities. The aim is to enroll 1,200 subjects. Due to the reasons described in section 6.1 and 6.2 the trial was stopped prior reaching the 1,200 subjects; hence 129 subjects were enrolled in total.

The trial is designed to provide a reasonable precision for an estimate of the number of subjects seroconverting for SARS-CoV-2 S protein RBD-specific antibodies and an acceptable rate of Grade 3 adverse reactions (defined as solicited local Grade 3 AEs, and solicited systemic or unsolicited Grade 3 AEs considered as related to the trial vaccine). Table 3 provides the estimate and 95% credibility interval for the observed numbers of subjects seroconverting for SARS-CoV-2 S protein antibodies for sample sizes of 150 (providing characteristics for a pre-defined co-morbidity) and 1,200 assuming a Beta (1.9, 0.1) priors

for seroconversion for SARS-CoV-2 S protein antibodies and Beta (0.5, 1.5) priors for Grade 3 adverse reactions are assumed.

Table 3 Estimate of Number of Subjects Seroconverting for SARS-CoV-2 S Protein Antibodies and 95% Credibility Interval (CI)

Rate (%)	Sample Size			
	150		1200	
	N	95% CI	N	95% CI
80	120	80.2 (73.5 - 86.1)	960	80 (77.7 - 82.2)
85	128	85.5 (79.5 - 90.6)	1020	85 (82.9 - 87)
90	135	90.1 (84.9 - 94.3)	1080	90 (88.3 - 91.6)
95	142	94.7 (90.6 - 97.6)	1140	95 (93.7 - 96.2)
100	150	99.9 (99.4 - 100)	1200	100 (99.9 - 100)

CI: credibility interval; N: subjects seroconverting for SARS-CoV-2 S protein antibodies

Table 4 below provides probabilities (in %) that the following 2 conditions are simultaneously met for assumed true adverse reaction rates and for assumed true rates of subjects seroconverting for SARS-CoV-2 S protein antibodies and for different sample sizes:

- There is a $\geq 80\%$ probability that the true rate of Grade 3 adverse reactions is $\leq 33\%$, and
- There is a $\geq 90\%$ probability that the true rate of subjects seroconverting for SARS-CoV-2 S protein antibodies is $> 95\%$.

For example, assuming a true adverse reaction rate of 20% and a true rate of subjects seroconverting for SARS-CoV-2 S protein antibodies of 97.5%, the 2 conditions are met with a probability of 68% and 100% sample sizes of 150 and 1,200 respectively.

Table 4 Probabilities (in %) for Assumed True Adverse Reaction Rates and for Assumed True Rates of Subjects with Seroconverting for SARS-CoV-2 S Protein Antibodies and Different Sample Sizes

True adverse reaction rate (%)	Sample Size					
	150			1200		
	True rate of subjects with seroconverting for SARS-CoV-2 S protein antibodies (%)			True rate of subjects with seroconverting for SARS-CoV-2 S protein antibodies (%)		
	95	97.5	100	95	97.5	100
5	13	68	100	10	100	100
10	13	68	100	10	100	100
15	13	68	100	11	100	100
20	13	68	100	10	100	100
25	11	61	91	10	100	100
30	6	32	47	10	92	92
35	1	6	8	0	1	1

8.4 Justification for Dose

CVnCoV will be evaluated at the dose level of 12 µg, defined based on clinical data from the ongoing trials CV-NCOV-001 and CV-NCOV-002.

8.5 End of the Trial Definition

A subject is considered to have completed the trial when he/she has completed all visits.

End of Trial is defined as the point at which the last subject has completed the last visit.

8.6 Randomization and Blinding/Unblinding

Not applicable, since this is an open-label, single-arm trial.

8.7 Inclusion/Exclusion Criteria

See sections 6.1 and 6.2 in the trial protocol.

9.0 Trial Endpoints

Any immunogenicity samples may also be used for assay validation and additional studies of the mechanism of action of the vaccine.

9.1 Primary Endpoints

The primary endpoints are stated in section 9.4.

9.2 Secondary Endpoints

The secondary endpoints are stated in section 9.4.

9.3 Exploratory Endpoints

The exploratory endpoints are stated in section 9.4.

9.4 Estimands

Based on the Protocol Amendment #1, a subset of endpoints will be presented. See Section 6.1, 6.2, 6.3 and 6.4 and Appendix 4 List of Abbreviated Scope Based on SAP Version 2.0 for additional details.

ENDPOINTS (subject level)	ESTIMANDS (population level)
Primary Safety	

The frequency, intensity, and duration of solicited local AEs on each vaccination day and the following 7 days.
 
The frequency, intensity, duration, and relationship to trial vaccination of solicited systemic AEs on each vaccination day and the following 7 days.
 
The occurrence, intensity and relationship to trial vaccination of unsolicited AEs on each vaccination day and the following 28 days.
 
The occurrence and relationship to trial vaccination of SAEs and AESIs throughout the trial.
	
In subjects who received at least one dose of CVnCoV vaccine and a post baseline vaccine safety assessment is available. Subjects receiving an authorized/licensed COVID-19 vaccine during the course of the trial will be censored at the day after intake. The primary safety will be analyzed with the safety analysis set.
 
The number and percentage of subjects overall and by co-morbidity:
 
Each solicited local AE within 7 days (after each trial vaccination by intensity and overall).
 
Each solicited systemic AE within 7 days after each trial vaccination by intensity, by relationship to trial vaccine and overall.
 
The mean duration in days by group with standard deviation of solicited AEs (within the solicited period, total duration).
 
At least 1 unsolicited AEs, at least 1 grade unsolicited AEs and each unsolicited AEs by SOC/PT occurring within 28 days after each trial vaccination and overall by causal relationship to trial vaccine and overall.
 
At least 1 SAE, or at least 1 AESI to vaccine overall by causal relationship to trial vaccine and overall.

ENDPOINTS (subject level)	ESTIMANDS (population level)
Primary Immunogenicity	

On Day 43:
 
The proportion of subjects seroconverting for SARS-CoV-2 S protein RBD antibodies, as measured by an immunoassay.
 
Individual SARS-CoV-2 S protein RBD-specific antibody levels in serum, as measured by an immunoassay.
 
Geometric mean titers (GMTs) of serum SARS-CoV-2 S protein RBD antibodies, as measured by an immunoassay.
 
In a subset of subjects*: the proportion of subjects seroconverting for SARS-CoV-2 neutralizing antibodies, as measured by an activity assay.
 
In a subset of subjects*: individual SARS-CoV-2 neutralizing antibody levels in serum, as measured by an activity assay.
 
In a subset of subjects*: GMTs of serum SARS-CoV-2 neutralizing antibodies, as measured by an activity assay.
	
In subjects who received dose 1 and dose 2 of trial vaccine and for whom the baseline blood sample for immunogenicity assessment and day 43 are available for analysis and no major protocol deviations expected to impact the immunogenicity outcomes. Subjects receiving an authorized/licensed vaccine during the course of the trial will be censored at the day after receiving the authorized/licensed vaccine. The primary immunogenicity will be analyzed with the per protocol immunogenicity subset.
 
Estimate of subjects seroconverted (SARS-CoV-2 spike protein-specific antibodies) with 95% credibility interval using prior beta (1.9, 0.1)
 
Number and percentage with exact 95% confidence intervals of subjects for who a seroconversion is observed (SARS-CoV-2 spike protein-specific antibodies)
 
Geometric mean of Fold Change from baseline with 95% CI of SARS-CoV-2 spike protein antibodies
 
Estimate of subjects seroconverted (SARS-CoV-2 neutralizing antibody levels in serum) with 95% credibility interval using prior beta(1.9, 0.1)
 
Number and percentage with exact 95% confidence intervals of subjects for who a seroconversion is observed (SARS-CoV-2 neutralizing antibody levels in serum)
 
Geometric mean of Fold Change from baseline with 95% CI of SARS-CoV-2 neutralizing antibody levels in serum

Secondary Immunogenicity	

On Day 29, Day 120, Day 211 and Day 393:
 
The proportion of subjects seroconverting for
	
In subjects who received at least 1 dose of CVnCoV vaccine and for whom the baseline blood sample and at least 1 additional blood sample are available for analysis. Subjects receiving an authorized/licensed COVID-19 vaccine during the course of the trial will be censored at the day after intake. The secondary immunogenicity will be analyzed with the immunogenicity set. Day 211 and Day 393 will not be measured.

ENDPOINTS (subject level)	ESTIMANDS (population level)

SARS-CoV-2 S protein RBD antibodies, as measured by an immunoassay.
 
Individual SARS-CoV-2 S protein RBD-specific antibody levels in serum, as measured by an immunoassay.
 
GMTs of serum SARS-CoV-2 S protein RBD antibodies, as measured by an immunoassay.
 
In a subset of subjects*, on Day 29 and Day 120:
 
The proportion of subjects seroconverting for SARS-CoV-2 neutralizing antibodies, as measured by an activity assay.
 
Individual SARS-CoV-2 neutralizing antibody levels in serum, as measured by an activity assay.
 
GMTs of serum SARS-CoV-2 neutralizing antibodies, as measured by an activity assay.
	
Estimate of subjects seroconverted (SARS-CoV-2 spike protein-specific antibodies) with 95% credibility interval using prior beta(1.9, 0.1)
 
Number and percentage with exact 95% confidence intervals of subjects for who a seroconversion is observed (SARS-CoV-2 spike protein-specific antibodies)
 
Geometric mean of Fold Change from baseline with 95% CI of SARS-CoV-2 spike protein antibodies
 
Estimate of subjects seroconverted (SARS-CoV-2 neutralizing antibody levels in serum) with 95% credibility interval using prior beta(1.9, 0.1)
 
Number and percentage with exact 95% confidence intervals of subjects for who a seroconversion is observed (SARS-CoV-2 neutralizing antibody levels in serum)
 
Geometric mean of Fold Change from baseline with 95% CI of SARS-CoV-2 neutralizing antibody levels in serum

Exploratory	

Occurrence of confirmed COVID-19 cases
 
Number of subjects with reverse transcription polymerase chain reaction (RT-PCR)-confirmed SARS-CoV-2 infection as measured by RT-PCR at clinically determined time points throughout the trial.
 
Number of subjects with asymptomatic SARS-CoV-2 infection as measured by serological titers of nucleocapsid antibodies on Day 1, Day 43, Day 120 and Day 393.
	
In subjects who received at least one dose of CVnCoV vaccine and a post baseline vaccine safety assessment is available. Subjects receiving an authorized/licensed COVID-19 vaccine during the course of the trial will be censored at the day after intake.
 
Number and percentage of subjects by co-morbidity at baseline and post-baseline time points with a positive RT-PCR result. This exploratory endpoint will be analyzed with the safety analysis set.
 
Number and percentage of subjects by co-morbidity at baseline and post-baseline with a positive RT-PCR result and/or infection defined by SARS-CoV-2 N-antigen and no COVID-19 symptoms. This exploratory endpoint will be analyzed with the immunogenicity set. Day 211 and Day 393 will not be measured.

	
CMI responses will not be analysed.

ENDPOINTS (subject level)	ESTIMANDS (population level)

CMI response
 
On Day 1, Day 29, Day 43 and Day 120 in peripheral blood stimulated with antigen in a subset of subjects*:
 
The SARS-CoV-2 S-specific T cell response, as measured by cytokine and chemokine expression after antigen stimulation using a standardized whole blood collection and culture system.
	

* The subset of subjects to participate in neutralizing activity and CMI response testing shall consist of approximately 25 subjects for each co-morbidity (up to a maximum of 175 subjects).

9.5 Population Sets

9.5.1 Immunogenicity Set

The Immunogenicity set will include all subjects who received at least 1 dose of CVnCoV and for whom the baseline blood sample and at least 1 additional blood sample are available for analysis.

9.5.2 Per Protocol Immunogenicity Subset (PPI)

The Per Protocol Immunogenicity subset (PPI) will include all subjects who:

- Received both doses within the windows defined in the protocol.
- Have no important protocol deviations expected to impact the immunogenicity outcomes as specified in the statistical analysis plan (SAP).
- Have not received medical treatments (such as blood products, immunoglobulin therapy) that may interfere with any of the proposed immunogenicity measurements.
- Have at least 1 blood sample collected starting at 14 days (Day 43) post-second vaccination available for analysis.

The PPI will be the primary analysis population for SARS-CoV-2 RBD of S protein antibody responses and SARS-CoV-2 viral neutralizing antibody responses.

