## 6.4 Vaccine Delay Recommendations

After enrollment, subjects may encounter clinical circumstances that warrant a delay of trial vaccine administration. These situations are listed below:

- Subjects with a clinically significant (Grade  $\geq 2$ ) active infection or other acute disease (as assessed by the Investigator and SARS-CoV-2 infection is either not clinically suspected or testing is negative) or body temperature  $>38.0^{\circ}\text{C}$  ( $>100.4^{\circ}\text{F}$ ), within 3 days of intended trial vaccination. Further dose administration should be delayed until the active infection or other acute disease has recovered to Grade  $\leq 1$  or the subject's body temperature has decreased to  $\leq 38.0^{\circ}\text{C}$  ( $\leq 100.4^{\circ}\text{F}$ ) for at least 3 days, if this still allows to vaccinate the subject as per the predefined interval. Body temperature should be measured orally and by using the thermometer provided to the subject at Visit 1.

- For subjects who develop laboratory-confirmed COVID-19 after the first dose but prior to receiving the second dose of CVnCoV, once the subject has recovered from COVID-19, the subject can be vaccinated with the second dose of CVnCoV, following two weeks of complete recovery if within the per protocol defined allowed time windows as specified in Table 1.
- Subjects who took antipyretic medication within 8 hours before intended trial vaccination (this is not applicable to the intake of low dose acetylsalicylic acid taken for prevention of cardiac disease).

In case of delay, the vaccination should take place within the allowed time windows specified in Table 1.

In case of any complications, the subsequent vaccination may be stopped or delayed.

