10.8.1.1 SARS-CoV-2 RBD of S Protein Antibodies

Seroconversion is defined as a fold increase above 1 in antibody titer against SARS-CoV-2 RBD of S protein regardless of the serostatus at baseline. In addition, 2-fold and 4-fold increases will be presented.

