10.9 Censoring Rules

Authorized/licensed vaccines are available to some subjects, and based on ethical reasons these subjects can decide whether they would like to receive the authorized/licensed vaccine. To avoid any study bias, subjects who are vaccinated with an authorized/licensed vaccine will be censored for safety and immunogenicity at the first day after receiving the authorized/licensed vaccine. The data collected from the censoring time point forward will be included and flagged in the listings output to identify corresponding data.

The following details are to be followed regarding censoring the day after receiving the authorized/licensed vaccine:

- Times are not relevant as neither authorized/licensed vaccine time nor case start time are collected.
- If authorized/licensed vaccine date is complete then censoring starts at first day after the authorized/licensed vaccine day.
- If authorized/licensed vaccine date is incomplete (only day missing) then censoring starts after this month.
- If authorized/licensed vaccine date is incomplete (month missing, year available) then censoring starts after this year.
- If authorized/licensed vaccine date is completely missing, then no censoring can be made.

As these imputations of incomplete authorized/licensed vaccine dates are not an ideal solution this is only to be considered as a fallback solution in case complete licensed vaccine dates cannot be retrieved and an interim workaround for unclean data during trial conduct.

All incomplete or missing authorized/licensed vaccine dates need to be queried.

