12.5 Important Protocol Deviations

Per PRA processes, protocol deviations data will be entered into PRA system of record (PSO). The trial team and the Sponsor will conduct ongoing reviews of the deviation data from PSO and the resulting set of evaluable subjects throughout the trial, adjusting the deviation criteria as seems appropriate.

Protocol deviation data will be reviewed prior to formal analysis (e.g. main, final) and important deviations leading to elimination of subjects from analysis sets will be identified. The detailed definitions of important protocol deviations leading to elimination of subjects from analysis sets will be provided in the final signed minutes of the data review meetings prior to each formal analysis.

A summary of important protocol deviation data will be created based on the SAS, displaying the number and percentage of subjects with any important protocol deviations and broken down by type of deviations. Protocol deviation data will also be listed.

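### The immunogenicity analysis has a rule for a licensed COVID-19 vaccine given after Day 1 but none for SARS-CoV-2 infection after Day 1, so antibody from infection can be counted as response to CVnCoV

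*SAP*

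**What the plan says.** SAP 12.7.2 analyses the primary humoral endpoints in the PPI. SAP 9.5.2, in line with Protocol 10.2, sets four conditions for entry:

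- dosing: "Received both doses within the windows defined in the protocol";
- no important protocol deviation that bears on immunogenicity;
- no interfering treatment: "Have not received medical treatments (such as blood products, immunoglobulin therapy) that may interfere with any of the proposed immunogenicity measurements";
- at least one usable sample from Day 43 onward.

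None of them mentions infection, a positive RT-PCR or a change in antibody to the nucleocapsid (N) protein.

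SAP 10.9 has a single trigger for censoring. Subjects who take an authorized or licensed vaccine "will be censored for safety and immunogenicity at the first day after receiving the authorized/licensed vaccine". The section gives avoidance of bias as the reason, and the immunogenicity estimands in SAP 9.4 repeat this trigger and add no other.

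For RBD antibodies, "Seroconversion is defined as a fold increase above 1 in antibody titer against SARS-CoV-2 RBD of S protein regardless of the serostatus at baseline". SAP 10.8.1.2 applies the same threshold to neutralizing antibodies.

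For laboratory-confirmed COVID-19 between doses, Protocol 6.4 says that "the subject can be vaccinated with the second dose of CVnCoV, following two weeks of complete recovery", provided the dose still falls in the permitted window.

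The data needed to recognise infection are collected. N antibody, which the vaccine cannot induce, is measured in all subjects (Protocol 9.2.2) at Day 1, Day 43, Day 120 and the end-of-trial visit, but not at Day 29. RT-PCR follows symptoms and a positive rapid test; after a negative rapid test it is discretionary (Protocol 9.3).

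**The concern.** A licensed vaccine and an infection pose the same problem for this analysis: each is a second source of RBD and neutralizing antibody, unrelated to CVnCoV. The plan deals with the first and is silent on the second. Since any rise above baseline counts as seroconversion, a rise caused by infection qualifies. SAP Appendix 4 even schedules the count of asymptomatic infections (Table 14.2.6.1) in the PPI itself, so the plan allows for infected subjects in its primary set.

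The primary immunogenicity objective is the humoral response to two doses of CVnCoV. No estimand says that antibody from infection should be part of it. At stake are the GMTs, the fold changes and, to a lesser extent, the seroconversion rates, overall and by co-morbidity.

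**Working it through.** **Plan's own figures.** With the Beta(1.9, 0.1) prior of SAP 8.3, the estimate is (x + 1.9)/(n + 2). For 135 of 150 this is 136.9/152 = 90.1%, with interval 84.9 to 94.3, as printed in SAP Table 3. The worked example (Grade 3 rate 20%, seroconversion 97.5%) recomputes to 67.7% at n = 150 and 100.0% at n = 1,200, against 68% and 100% printed. These tables are sound and the present point does not touch them. They supply only 97.5% as a planning rate.

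**Which infections stay in the PPI.**

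- *Detected between doses.* The Day 29 window is -3/+14 days, so the latest in-window dose is Day 43. Two weeks after full recovery then means recovery by Day 43 - 14 = Day 29. Subjects recovered by then can stay in. Later recoveries fail the dosing condition and drop out.
- *Undetected between doses.* These stay in.
- *After dose 2.* All stay in, because the dosing condition is already met. The scheduled exposure from dose 2 is 14 days (-2/+4) to the Day 43 sample and 91 days to Day 120.

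**Size.** The documents give neither of the two inputs needed, so both are assumptions:

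- q, the share of the analysed subjects infected before the sample: 2%, 5% or 10%;
- k, the factor by which infection multiplies the titre: 5 to 20.

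*GMT.* If a share q has its log titre raised by log k, the mean log titre rises by q log k, so the GMT ratio is k^q. Fold change from baseline carries the same factor.

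| q | k = 5 | k = 10 | k = 20 |
|---|---|---|---|
| 2% | 1.03 | 1.05 | 1.06 |
| 5% | 1.08 | 1.12 | 1.16 |
| 10% | 1.17 | 1.26 | 1.35 |

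*Small stratum.* 129 enrolled over seven co-morbidities is 129/7 = 18.4. This is only an illustration: strata overlap (SAP 12.0), and 129 is the number enrolled, not the PPI. With 18 subjects, one infection gives 5^(1/18) = 1.09 to 20^(1/18) = 1.18. Two give 1.20 to 1.39.

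*Seroconversion.* Let p be the rate from vaccine alone. If every infected subject converts, and infection is unrelated to response, the observed rate is p + (1 - p)q, so the bias is (1 - p)q. In percentage points:

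| p | q = 2% | q = 5% | q = 10% |
|---|---|---|---|
| 97.5% | 0.05 | 0.125 | 0.25 |
| 90% | 0.2 | 0.5 | 1.0 |
| 70% | 0.6 | 1.5 | 3.0 |

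The same formula applies to the 2-fold and 4-fold thresholds, with p taken as the rate at that threshold.

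**The case against.** The case for leaving the plan alone has several parts.

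- **The seroconversion effect is small.** This stands. With so low a threshold, most infected subjects would have counted anyway.
- **Dose timing already removes some infections.** This stands in part. Confirmed infection is a listed reason to stop dosing (Protocol 8.1), and late recovery takes the subject out of the PPI. Undetected infections and those after dose 2 are not reached.
- **Data review could exclude infected subjects.** "The detailed definitions of important protocol deviations leading to elimination of subjects from analysis sets will be provided in the final signed minutes", so the criteria are not fixed in the SAP, although SAP 9.5.2 says they are. Infection is also not a protocol deviation.
- **Infections will be visible in the outputs.** Counts and listings are planned in Appendix 4, but they do not change the titre summaries. SAP 6.4 also says that the analysis of confirmed COVID-19 cases will not be performed, while SAP 12.7.3 includes it.
- **Baseline serostatus is handled.** The split in Protocol 10.3.5.2 concerns infection before Day 1, not after.
- **Censoring can itself mislead.** This stands. If poor responders are more likely to be infected, removing them biases the remaining results upward. That is a reason to show both analyses rather than to replace one with the other.
- **Everything is descriptive.** This stands. No test or error rate is affected.

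**Conclusion.** The point holds as a missing rule, not as a wrong figure. The plan gives a licensed vaccine a censoring rule and gives infection none, and no other section closes the gap. If infections occur, GMT and fold change are overstated by the factors shown, which rest on assumed q and k. The exposure is greatest at Day 120, because of the longer follow-up, and in small co-morbidity strata.

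A reader might infer more than the documents support:

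- *That the reported titres will be inflated.* This depends on infections occurring, and the documents give no rate.
- *That a 10-fold rise is the right multiple.* No multiple is given, so only a range can be shown.
- *That one infected subject in a stratum of 18 adds 1/18 = 5.6 points to seroconversion.* That is true only if the subject would otherwise not have responded. With a 2.5% to 10% chance of non-response, the expected addition is 0.14 to 0.56 points.
- *That every infected subject stays in the PPI.* The dosing condition removes some of them.

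**What to change.** Add to SAP 10.9, for immunogenicity only: results are censored from the first positive RT-PCR after Day 1, or from the first N-positive sample in a subject who was N-negative at Day 1, that sample included. Report the PPI results with and without this censoring at Day 43 and Day 120, with the number of subjects removed at each, overall and by co-morbidity. Carry the rule into the estimands in SAP 9.4.

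Reconcile two related texts at the same time: SAP 6.4 with 12.7.3 on whether COVID-19 cases are analysed, and the introduction to SAP 10.8.1, which makes seroconversion depend on N antibody status, with 10.8.1.1 and 10.8.1.2, which do not.

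The change needs no new data: one rule and a second set of immunogenicity summaries. Its limits should be stated in the SAP:

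- some primary Day 43 observations may be lost, not only later ones;
- censoring may selectively remove poor vaccine responders, which is why both results are shown;
- at Day 29 only RT-PCR can trigger the rule, because N antibody is not measured there;
- subjects N-positive at Day 1 cannot meet the N criterion, so only RT-PCR can identify a new infection in them.
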